5.1. Within-Subject Comparisons

To evaluate the effectiveness of TMS over time:

- Wilcoxon signed-rank test will be used for paired comparisons of non-parametric variables between baseline and subsequent time points (e.g., Pre-VAS vs Day 5, Day 10, etc.).
- **Paired t-tests** will be used only if variables demonstrate normal distribution.

5.2. Repeated Measures Analysis

- **Repeated measures ANOVA** will be conducted to evaluate the impact of the intervention over multiple time points for continuous outcome variables such as VAS, FACT-G, and TOI.
- When the sphericity assumption is violated (tested via **Mauchly's test**), Greenhouse-Geisser or Huynh-Feldt corrections will be applied.
- Effect sizes (partial eta squared) and observed power will be reported for all significant outcomes.

6. Multivariable Analysis

• If sample size allows, analysis of covariance (ANCOVA) or linear mixed models may be considered to adjust for potential confounders such as age, sex, and baseline pain level.

7. Handling of Multiple Comparisons

• Due to the exploratory nature of the study and small sample size, no formal adjustment for multiple comparisons will be applied. However, results will be interpreted with caution, and this limitation will be noted in the final report.

8. Subgroup Analyses

• No pre-specified subgroup analyses are planned due to limited sample size.

9. Deviations from Planned Analysis

• Any deviations from this pre-specified plan will be documented and justified in the final study report.

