Cover page study protocol

Study Title: Application of transcranial magnetic stimulation treatment in patients with oncological neuropathic pain to evaluate effectiveness on pain and quality of life

NCT number: 05480410

Date of the document: 1/02/2022

Study protocol

The protocol will be structured according to the national institute of health, the statements described by the clinical trial database and the SPIRIT declaration, which include detailed study description and design, intervention, outcome measures and individual participant data and results sharing statement.

10 patients will receive 20 sessions of transcranial magnetic stimulation using the MagVenture Mag Pro R20 device. These sessions will be conducted daily from Monday to Friday, lasting 20 minutes each, at an intensity of 81% with a motor threshold of 90 A/ns.

A pre-post design without a control group will be used to evaluate 2 elements: pain and quality of life.

The evaluation moments will be as follows:

- Pretest: Quality of life and pain will be assessed using the Visual Analog Scale (VAS) and the Brief Pain Inventory (BPI).

- Each session: Pain will be assessed using the VAS.

- Each week: Pain will be assessed using the BPI.

- Immediate Posttest: Quality of life and pain will be assessed using both scales.

- Posttest at 1 month and 3 months: Quality of life and pain will be assessed using both scales.

The patients will meet the following inclusion criteria: female or males aged over 18 and under 75 years, any stage of cancer, chemotherapeutic treatment consisting of taxanos or oxaliplatin, neuropathic pain with a minimum grade 2 severity based on the National Cancer Institute Common Terminology Criteria for Adverse Events scale (NCI-CTCAE, version 5.0), and a mean 2 score or above in a visual analogue scale (VAS) of pain. We will exclude patients with any psychiatric disorder including major depression; history of seizure, epilepsy, stroke and intracranial metallic devices. Patients should agree to avoid any extra use of medication or to make any changes to their pharmacological plan during the trial.

The aim of collecting these variables is to gather data and conduct statistical analysis to evaluate the effectiveness of transcranial magnetic stimulation on pain and quality of life in patients with neuropathic pain secondary to oncological treatment.

TEST 1: Pain

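### SAP 5.2 makes the sphericity correction depend on Mauchly's test, an unreliable screen with 10 patients; one correction and the ANOVA time points should be fixed in advance

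*SAP*

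**What the plan says.** SAP 5.2 plans a repeated measures ANOVA "to evaluate the impact of the intervention over multiple time points for continuous outcome variables such as VAS, FACT-G, and TOI". It does not list the time points. The correction is conditional: "When the sphericity assumption is violated", with Mauchly's test as the check, "Greenhouse-Geisser or Huynh-Feldt corrections will be applied". Nothing says which of the two corrections takes precedence, or what happens if Mauchly's test cannot be computed. SAP Section 2 sets significance at p < 0.05 and restricts analysis to complete cases.

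The protocol fixes the size and the schedule:

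- Size and design: "10 patients will receive 20 sessions of transcranial magnetic stimulation", and "A pre-post design without a control group will be used".
- VAS: pretest, then "Each session: Pain will be assessed using the VAS", then an immediate posttest.
- BPI: "Each week: Pain will be assessed using the BPI", besides the pretest and posttests.
- Follow-up: "Posttest at 1 month and 3 months: Quality of life and pain will be assessed using both scales".

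The only VAS days that the SAP names (days 5 and 10, as examples) are in Section 5.1, for the paired tests.

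**The concern.** The F test for time in a repeated measures ANOVA rejects too often when sphericity does not hold and no correction is made. SAP 5.2 relies on a preliminary test to decide whether to correct. With 10 patients or fewer, a non-significant Mauchly result is weak evidence of sphericity, yet the rule treats it as permission to use the uncorrected test. Above a certain number of time points the preliminary test does not exist at all, and the protocol collects far more VAS values than that number. The open choice between two corrections adds a decision that could be made after the results are seen. At stake is whether a reported time effect on VAS, FACT-G or TOI carries the 5% error rate that the SAP states.

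**Working it through.** The documents give no error rate or power for this analysis, so there is no stated figure to reproduce.

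**Inputs from the documents.** n = 10 in one group, so ν = n − 1 = 9. Alpha is 0.05.
- VAS occasions: 1 pretest + 20 sessions + 1 immediate posttest + 1 month + 3 months = 24, or 23 if the immediate posttest is the session-20 value.
- Quality of life: 4 occasions. I take TOI to follow the same visits.
- Weekly VAS: about 5 levels (pretest and four weeks), or 7 with both follow-ups.
- BPI, if analysed this way: 7 or 8 levels.

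**Input assumed.** The documents give no within-patient covariance. I used first-order autoregressive correlation of 0.5, 0.7 and 0.9, and a constant correlation of 0.6 with the SD doubling over time.

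**1. When Mauchly's test exists.** For k levels let p = k − 1 and let S be the p × p covariance matrix of orthonormal contrasts. The statistic is W = det(S) / (tr(S)/p)^p. The rank of S is at most min(p, n − 1).
- k = 10: p = 9, rank 9, computable.
- k = 11: p = 10, rank 9, so det(S) = 0.
- k = 21: p = 20, rank 9, so det(S) = 0.
- k = 24: p = 23, rank 9, so 23 − 9 = 14 eigenvalues are zero and det(S) = 0.

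With n = 10 the ceiling is therefore 10 levels. It falls by one for each patient lost to complete-case analysis. This step needs no assumption about covariance.

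**2. How the conditional rule performs where the test exists.** I simulated multivariate normal data with no change over time, 6,000 runs per scenario.
- Mauchly: X = −ν·d·ln W with d = 1 − (2p² + p + 2)/(6pν), referred to chi-square on p(p+1)/2 − 1 df with the second-order term.
- Greenhouse-Geisser (GG): ε = tr(S)² / (p·tr(S²)), with F referred to pε and pνε df.
- Huynh-Feldt (HF): min[1, (npε − 2)/(p(ν − pε))] in place of ε.

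The Monte Carlo standard error near 5% is √(0.05 × 0.95/6000) ≈ 0.003.

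Results at n = 10 (ranges over the four assumed structures; all columns after detection are type I error):

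| Levels | True ε | Mauchly detects | Never corrected | If Mauchly significant: GG | If Mauchly significant: HF | Always GG | Always HF |
|---|---|---|---|---|---|---|---|
| 4 | 0.68-0.87 | 14-37% | 0.058-0.064 | 0.053-0.058 | 0.056-0.059 | 0.037-0.043 | 0.050-0.054 |
| 5 | 0.58-0.87 | 13-51% | 0.059-0.088 | 0.055-0.070 | 0.057-0.075 | 0.034-0.046 | 0.052-0.066 |
| 7 | 0.44-0.86 | 13-74% | 0.058-0.101 | 0.054-0.068 | 0.056-0.074 | 0.026-0.039 | 0.050-0.060 |
| 8 | 0.40-0.86 | 15-80% | 0.060-0.118 | 0.055-0.066 | 0.059-0.076 | 0.023-0.046 | 0.052-0.066 |

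The rule as written therefore has a type I error of about 0.053-0.076. The 74% and 80% detection rates arise only at true ε of about 0.4.

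With 8 complete cases, detection falls to 10-25% (4 levels), 10-37% (5) and 12-54% (7), and the conditional rule runs at 0.055-0.084 over 4-7 levels. At 8 levels with 8 cases, Mauchly's test rejects 19% of the time even when sphericity holds, so its result there means little.

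**3. If a session-level series were entered and left uncorrected.** At 21 and 24 levels (autoregressive 0.7 and 0.9, 3,000 runs), type I error is 0.123-0.173 uncorrected, 0.016-0.040 with GG and 0.059-0.075 with HF. A wider set of assumed structures at 24 levels (6,000 runs) gave 0.077-0.192 uncorrected and 0.007-0.035 with GG.

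**The case against.** The strongest reply is that the serious failure belongs to an analysis that the SAP does not specify. A reader might infer from the visit schedule that all 24 VAS values enter the ANOVA. The documents do not support that: the protocol lists when data are collected, not the levels of the ANOVA factor, and the day 5 and day 10 examples in SAP 5.1 point to weekly values. Those examples concern the paired tests, so they are a hint and do not settle what SAP 5.2 does. The 8-19% figure must stay conditional.

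A reader might also infer that the uncorrected F test would be used whenever Mauchly's test is unavailable. The SAP is silent on that case. The analyst could still report a corrected p-value, and Section 9 requires deviations to be justified.

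Nor can this be called a threat to the trial's main pain result. No primary endpoint is named, Section 5.1 assigns effectiveness over time to paired tests that need no sphericity assumption, and Section 4 sends non-normal variables to non-parametric methods.

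Finally, on the weekly reading the excess error is small, and detection is lowest mainly where the violation is mild. The study is described as exploratory, with cautious interpretation promised. All of this stands and limits the point to an inexpensive improvement. The caution in Section 7 concerns multiple comparisons, however, and does not repair the error rate of a single F test. The open choice of correction remains whichever time points are used.

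**Conclusion.** The point holds in a limited form. Making the correction depend on Mauchly's test is a weak rule at this sample size. In series of 4-8 levels it lets the type I error rise to about 5-7.6% with 10 patients, and up to 8.4% in the scenarios with 8 complete cases. It also leaves the choice between Greenhouse-Geisser and Huynh-Feldt to be made after the data are seen. The larger inflation, about 8-19%, would arise only if more than 10 VAS levels were entered and the F test left uncorrected; the SAP neither plans nor rules that out. The ceiling of 10 levels is algebra. Detection and error rates rest on normal data and assumed covariances, because the documents give none. The change is worth making because it is cheap, not because the planned analysis is shown to be invalid.

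**What to change.** In SAP 5.2, replace the conditional sentence with: *Greenhouse-Geisser-corrected p-values will be used for every repeated-measures ANOVA, whatever the result of Mauchly's test.* Add a list of the time points for each outcome, with fewer VAS levels than complete cases. An example is pretest, end of weeks 1 to 4, 1 month and 3 months: 1 + 4 + 2 = 7 levels. State explicitly whether the week-4 level is the last session value or the immediate posttest; using both makes 8 levels.

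The cost is two short edits, and the corrected p-value comes from the same analysis. Greenhouse-Geisser is somewhat conservative here: about 2-5% actual error at 4-8 levels when sphericity is violated, and as low as 1.5% at 8 levels when it holds exactly. Always using Huynh-Feldt would also close the open choice and runs at 5.0-6.6% at 4-8 levels; Greenhouse-Geisser is preferred because it stayed below 5% in every scenario simulated. Keeping the list short matters even with that correction, since at 21-24 levels its error falls to 0.7-4.0%. If results have already been seen, record the change as a deviation under SAP Section 9.

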Statistical Analysis Plan (SAP)

Study Title: Effectiveness of rTMS on Pain and Quality of Life in Patients With Cancer Neuropathic Pain

NCT Number: NCT05480410 **Version Date**: 5/06/2024

1. Objectives of the Statistical Analysis

The primary objective of the statistical analysis is to assess the effectiveness of transcranial magnetic stimulation (TMS) in reducing oncological neuropathic pain and improving quality of life in patients with cancer. This includes analyzing changes in Visual Analogue Scale (VAS), Brief Pain Inventory (BPI), and quality of life indicators (FACT-G and NTX subscales).

2. General Considerations

- All analyses will be conducted using IBM SPSS Statistics software (version specified in final results).
- A p-value < 0.05 will be considered statistically significant.
- No data imputation will be performed; all analyses will be based on observed values (complete case analysis).
- Assumptions required for each test (e.g., normality) will be tested and reported.

3. Descriptive Analyses

- Continuous variables (e.g., age, VAS scores, BPI scores) will be described using means, standard deviations, medians, ranges, and percentiles, depending on the distribution of the data.
- Categorical variables (e.g., sex) will be reported as frequencies and percentages.

4. Assessment of Normality

- The normality of continuous outcome variables will be tested using the **Shapiro-Wilk** test.
- If variables are not normally distributed, non-parametric methods will be used for inferential comparisons.

5. Inferential Analyses

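### The SAP assures a standardized effect size only for significant outcomes and plans no confidence interval for the change from baseline

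*SAP*

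**What the plan says.** - SAP section 5.2, on the repeated measures ANOVA: "Effect sizes (partial eta squared) and observed power will be reported for all significant outcomes". It also plans that "Greenhouse-Geisser or Huynh-Feldt corrections will be applied" when Mauchly's test rejects sphericity.
- SAP section 2 sets the threshold: "A p-value < 0.05 will be considered statistically significant". It also restricts analyses to complete cases.
- SAP section 1 puts change within the objective: "This includes analyzing changes in Visual Analogue Scale (VAS), Brief Pain Inventory (BPI), and quality of life indicators (FACT-G and NTX subscales").
- SAP section 3 says continuous variables "will be described using means, standard deviations, medians, ranges, and percentiles", with no condition on significance.
- SAP section 5.1 names the Wilcoxon signed-rank test and the paired t-test for comparisons with baseline. It names no estimate of the change and no interval.
- SAP section 6 makes ANCOVA or mixed models optional and names no interval.
- SAP section 7: "Due to the exploratory nature of the study and small sample size, no formal adjustment for multiple comparisons will be applied".
- The Protocol fixes 10 patients and no control group, and gives no power, effect size or standard deviation. It assesses quality of life at four moments: pretest, immediate posttest, 1 month and 3 months.

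**The concern.** A small study that its own SAP calls exploratory is useful mainly for how large the change was and how precisely it was measured. The section 5.2 sentence ties the only planned standardized effect size to p < 0.05. With 10 patients only large observed effects pass that threshold, so the values sure to be reported are a selected set and too high on average. How much too high depends on true power, which nobody knows.

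Observed power does not help the reader judge this. It is fixed by the p-value and the degrees of freedom, and restricting it to significant results gives it a floor.

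No interval is planned to put beside any of these figures. A reader could therefore be left with an inflated partial eta squared, a comfortable-looking power figure, and no statement of precision.

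**Working it through.** The plan states no power or effect-size figure, so there is nothing of its own to reproduce. The case worked is quality of life at four time points in 10 complete patients.

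**Inputs.** n = 10 and k = 4 (Protocol); alpha = 0.05 (SAP section 2). Assumed: no missing visits, true power as listed, and two-sided intervals. Degrees of freedom are k − 1 = 3 and (k − 1)(n − 1) = 27.

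**Smallest partial eta squared that can be significant (sphericity).** Critical F(3, 27) = 2.960. Floor = 3F/(3F + 27) = 8.881/35.881 = 0.248.

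**Effect of selecting on significance.** The population value is ncp/(ncp + n(k − 1)) = ncp/(ncp + 30), where ncp is the noncentrality giving the stated power. The means come from simulated noncentral F draws.

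| True power | ncp | Population value | Mean, all results | Mean, significant results |
|---|---|---|---|---|
| 10% | 0.90 | 0.03 | 0.12 | 0.31 |
| 50% | 6.65 | 0.18 | 0.26 | 0.35 |
| 80% | 12.61 | 0.30 | 0.36 | 0.40 |
| 95% | 19.90 | 0.40 | 0.45 | 0.46 |

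The upward bias has two parts. The bias of partial eta squared itself (all results minus population) is 0.09, 0.08, 0.06 and 0.05 down the table. The part added by selection (significant minus all) is 0.19, 0.09, 0.04 and 0.01. Selection dominates at low power. At 80% and 95% power most of the bias is the statistic's own. With no effect at all, partial eta squared still averages 3/(3 + 27) = 0.10.

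**Floor on observed power.** Set the noncentrality to its observed value at the threshold, 3 × 2.960 = 8.881. Then 1 − ncF(2.960; 3, 27, 8.881) = 0.63. For the sphericity corrections, multiply both degrees of freedom by epsilon and use ncp = 3 × epsilon × critical F:

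| Epsilon | Critical F | Partial eta squared floor | Observed-power floor |
|---|---|---|---|
| 0.7 | 3.473 | 0.278 | 0.59 |
| 0.5 | 4.101 | 0.313 | 0.56 |
| 1/3 (lower bound) | 5.117 | 0.362 | 0.52 |

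Under sphericity and 10% true power, observed power among significant results averages 0.77.

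**Precision of the change.** The 95% half-width for a mean change is t(0.975, n − 1)/√n in SDs of the change: 2.262/√10 = 0.72 at n = 10 and 2.365/√8 = 0.84 at n = 8. To get this from the section 3 descriptives, a reader needs the pre-post correlation r, which is not planned for reporting. With equal SDs assumed, the half-width in score SDs is 0.715 × √(2(1 − r)): 0.85 at r = 0.3, 0.72 at 0.5, 0.45 at 0.8 and 0.32 at 0.9. The same descriptives fit all four.

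**The case against.** The strongest reply is that the plan leaves less unreported than it first appears to.

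- **Raw effects are available.** A reader might infer that nothing about size is reported unless p < 0.05. The documents do not support that. Section 3 is unconditional, and a difference in points on a 0–10 VAS is an effect size, arguably the clearest one. Only the standardized measure depends on significance. This stands, with one limit: section 3 lets the summary follow the distribution, and a difference of medians is not the median change.
- **The sentence sets a minimum.** It does not forbid reporting other outcomes. This also stands: the SAP is silent here, so a charge of planned suppression would go too far.
- **Precision may be recoverable.** Where a paired t-test is used, the standard error is the mean difference divided by t, and the interval follows whatever the correlation. This stands only if the t value or an exact p-value is published, which the SAP does not promise. It does not work for the Wilcoxon test.
- **At high power the inflation is small.** This is true of the part due to selection. It is not true of partial eta squared against its population value, and reporting every result would not remove that remainder.
- **Observed power drives no decision, and section 7 already promises caution.** Both are correct. But that caution concerns multiplicity, and it gives the reader no number to be cautious with.

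**Conclusion.** The point holds in a narrow form. The SAP assures partial eta squared and observed power only for significant outcomes, and it plans no interval for the change anywhere. The precision of the paired change is therefore not assured: it cannot be derived from the descriptives, it can be recovered from a paired t-test only if t or an exact p-value is given, and it cannot be recovered from the Wilcoxon test.

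In the case worked, selection adds about 0.19 to mean partial eta squared at 10% true power and about 0.01 at 95%. Observed power beside a significant result is at least 0.63, or 0.52 under the lower-bound correction, so it cannot show that true power was low. The bias figures assume sphericity, 10 complete patients and the stated true powers. The floors need no assumption about true power.

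A reader might go further and conclude that non-significant results will be withheld, or that reporting every partial eta squared would make it unbiased. The text does not support the first, and the calculation contradicts the second. For a ten-patient, uncontrolled, exploratory study this should be changed, but it ranks low among such changes.

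**What to change.** Replace the section 5.2 sentence with:

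> For every outcome and every comparison made under section 5.1, regardless of p-value, the change from baseline will be reported with its 95% confidence interval and number of patients (mean change with t interval where the paired t-test is used; Hodges-Lehmann estimate with its interval where the Wilcoxon test is used). Partial eta squared will be reported for every repeated measures ANOVA, whether or not significant. Observed power will not be reported.

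The change with its interval should lead the results, because partial eta squared is biased upward at this sample size even when nothing is selected.

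**Cost.** One SAP sentence, plus an estimate and an interval for each comparison. No new data are needed.

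**Downsides.**
- The intervals are wide (half-width 0.72 SD of the change at 10 patients, 0.84 at 8) and unadjusted for multiplicity.
- With 5 or fewer complete pairs no exact 95% Hodges-Lehmann interval exists: the highest level at 5 pairs is 1 − 2/2⁵ = 93.75%.
- Section 4 selects the test by Shapiro-Wilk, so the estimator may switch between visits for the same outcome.
- An interval does nothing about the lack of a control group.
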